### 10.4 ADVERSE EVENT FOLLOW-UP

Until the participant reaches the final scheduled follow-up visit, any new AEs, as well as follow-up information for ongoing AEs, must be recorded. For participants who withdraw prematurely, AEs should be followed until 30 days after last study visit.

### 10.5 REPORTING OF PREGNANCY

Pregnancy, in and of itself, is not regarded as an AE. A confirmed pregnancy in a participant (by urine or blood test) should be reported to the CRO as soon as the investigator has been made aware of the pregnancy. The decision on whether to remove the implant and withdraw the participant from the study will be made by the investigator and the participant following consultation with the sponsor. The investigator will use his/her expert judgment, based on an assessment of the potential benefit/risk to the participant, to determine if it is in the participant’s best interest to continue participation in the study.

A pregnancy in the partner of a participant should also be reported to the investigator who will in turn notify the CRO as soon as possible.

The pregnancy should be followed until birth. The outcome of all such pregnancies (ie, spontaneous miscarriage, elective termination, normal birth, or congenital abnormality) must be documented and followed-

up on a form that will be provided by the CRO. The pregnancy will be followed to term and the outcome, including any premature termination, must be reported to the CRO. All live births must be followed for a minimum of 30 days or to the first well-baby visit. All reports of congenital abnormalities/birth defects and spontaneous abortions/miscarriages should be reported as an SAE for this study. Elective abortion procedures, without complications, should not be considered as AEs.

## 11. SERIOUS ADVERSE EVENT

### 11.1 DEFINITION OF SERIOUS ADVERSE EVENT

An SAE is any event that meets any of the following criteria:

- Death
- Life-threatening
- Inpatient hospitalization or prolongation of existing hospitalization
- Persistent or significant disability/incapacity
- Congenital anomaly/birth defect in the offspring of a participant who received NT-501
- Other: Important medical events that may not result in death, be life-threatening, or require hospitalization, may be considered an SAE when, based upon appropriate medical judgment, they may jeopardize the participant and may require medical or surgical intervention to prevent one of the outcomes listed in this definition.

#### Definition of Terms

**Life-threatening:** An AE is life-threatening if the participant is at immediate risk of death from the event as it occurred; ie, it does not include a reaction that if it had occurred in a more serious form might have caused death. For example, drug-induced hepatitis that resolved without evidence of hepatic failure would not be considered life-threatening even though drug-induced hepatitis can be fatal.

**Hospitalization:** AEs requiring hospitalization should be considered SAEs. Hospitalization for elective surgery or routine clinical procedures that are not the result of an AE (eg, elective surgery for a pre-existing condition that has not worsened) need not be reported as AEs or SAEs. If anything untoward is reported during the procedure, that occurrence must be reported as an AE, either serious or nonserious according to the usual criteria.

In general, hospitalization signifies that the participant has been detained (usually involving at least an overnight stay) at the hospital or emergency ward for observation and/or treatment that would not have been appropriate in the physician's office or outpatient setting. When in doubt as to whether 'hospitalization' occurred or was necessary, the AE should be considered serious.

**Disability/incapacity:** An AE is disabling or incapacitating if the experience results in a substantial and/or permanent disruption of the participant's ability to carry out normal life functions.

### 11.2 REPORTING SERIOUS ADVERSE EVENTS

The investigators will report data on all SAEs within 24 hours of site awareness of the event. If there are technical difficulties when entering the event into the EDC system, the SAE will be reported to the contract

research organization (CRO) via fax communication or safety group email; the fax numbers and email address will be provided in the regulatory binder. All information reported by fax or email will need to be entered in the data system when it is available. All SAEs should be reported to local IRBs/independent ethics committees (IECs) per local IRB/IEC requirements.

The medical monitor will review each SAE report and will determine whether the SAE must be reported to the Food and Drug Administration (FDA)/regulatory authorities on an expedited basis. The final decision for disposition regarding reporting to the FDA and other regulatory authorities rests with the sponsor or their designee. The IND sponsor or their designee is responsible for submitting the SAE reports to FDA/regulatory authorities. The sponsor will ensure that the data and safety monitoring committee (DSMC; see Section 14.3) receives any safety report submitted to FDA/regulatory authorities. The CRO will maintain copies of any SAE reports submitted to FDA/regulatory authorities by the sponsor.

The CRO will provide expedited reports to the principal investigator at each individual site to submit to their respective IRB/IEC. Events that are serious, related to therapy, and unexpected (serious unexpected suspected adverse reaction [SUSAR]) will be reported to FDA/regulatory authorities within 15 days or within 7 days for deaths and for events deemed life-threatening by the investigator (per 21 CFR 312.32).

All SAEs will be followed until resolution or until stability is reached. In rare instances, this may include following the participant after completion of the study. Every attempt must be made by the investigator to follow SAEs that are not resolved or medically stable within 30 days of the last study visit until they become resolved or medically stable.

### 11.3 NOTIFYING FDA/REGULATORY AUTHORITIES

After the SAE has been reported by the principal investigator and assessed by the IND sponsor, the IND sponsor or their designee must report the event to the appropriate regulatory authorities using 1 of these 2 options:

- Standard reporting (report in the annual report). This option applies if the AE is classified as one of the following:
  - Serious, expected, suspected adverse reaction (serious, expected, and related)
  - Serious and not a suspected adverse reaction (serious and not related)
- Expedited reporting. This option applies if the AE is classified as SUSAR (serious, unexpected, and related).

The sponsor must report an AE as a suspected adverse reaction (related AE) only if there is evidence to suggest a causal relationship between the study treatment and the AE, such as:

- A single occurrence of an event that is uncommon and known to be strongly associated with study treatment
- One or more occurrences of an event that is not commonly associated with study treatment, but is otherwise uncommon in the population exposed to the study treatment
- Aggregate analysis of specific SAEs observed in a clinical trial (such as known consequences of the underlying disease or condition under investigation or other events that commonly occur in the study population independent of study treatment) that indicates those events occur more frequently in the study treatment group than in a concurrent or historical control group

- Any findings from clinical or epidemiological studies, analysis of data pooled across multiple studies, published or unpublished scientific papers, or from animal or in vitro testing that would result in a safety-related change in the protocol, informed consent, general investigational plan section of the IND, or other aspects of the overall conduct of the trial

## 11.4 REPORTING SAES TO THE DSMC

The CRO will provide the DSMC with the data for all SAEs on an ongoing basis as described in the charter.

The investigator will ensure the timely dissemination of all AE information, including expedited reports and DSMC safety reviews, to the IRB and IEC in accordance with applicable local regulations and guidelines.

## 12. STATISTICS

### 12.1 GENERAL PROCEDURES

This is a Phase 3 study to evaluate the efficacy and safety of NT-501 compared with the sham procedure for the treatment of MacTel.

One eligible study eye from each participant will be randomized in a 1:1 ratio as follows:

- Surgery to receive 1 NT-501 device implant delivering a nominal CNTF dose of 20 ng/device/day
- Sham surgery

Randomization: Two treatment assignments with a 1:1 (NT-501 surgery: sham procedure) allocation scheme for each of the 2 protocols (Protocol A and Protocol B). The actual treatment assignment (NT-501 surgery or sham procedure) will be shown within Advantage eClinical. Randomization is unrestricted. One randomization list per protocol will be generated. There will be no stratification for prognostic factors.

The biostatistician will prepare detailed statistical procedures, listings, table shells and figures in a separate statistical analysis plan (SAP). The following key components will be considered, and a detailed description will be documented in the SAP:

- Descriptions of primary and secondary endpoints and how they will be measured
- Statistical methods and any applicable alternative methods (eg, model nonconvergence) used to analyze the endpoints
- Justifications for sample size calculations
- Multiple testing approaches
- Approaches to account for missing data

A biostatistician will perform statistical analyses as agreed with the sponsor according to the SAP. Any additional or supplemental data analyses performed independently by an investigator shall be submitted to the sponsor for review.

### Analysis Populations:

The modified intention-to-treat (mITT) population will consist of all randomized participants who received surgery (NT-501 or sham surgery), all of whom will be analyzed in the treatment group to which they were assigned regardless of compliance or other protocol deviations.

The per-protocol (PP) population will be a subset of the mITT population and will include all available data from participants who follow the protocol without major protocol deviation. The PP population will be used for analyses of primary and key secondary efficacy variables. Participants will be analyzed according to the randomized treatment. The determination of all protocol violations and any data excluded from the efficacy analysis will be made prior to locking the final database.

The safety population will include the data from all randomized participants who receive any treatment and have at least 1 safety measurement. Participants will be analyzed in the group according to the treatment received, and no subjects (or data) will be excluded from this dataset because of protocol violations that occur during the study.

The efficacy analysis will be conducted on the mITT population and on the PP population. Safety analyses will be performed using the safety population. The handling of participants with missed visits or visits occurring outside the specified windows will be considered in the SAP.

If both eyes of a participant qualify for the study, the study eye will be selected using the centralized randomization process.

Continuous variables will be summarized using descriptive statistics (n, mean, standard deviation [SD], median, minimum, and maximum), and categorical variables will be summarized using the count and percentage of participants in each category.

### Significance Level:

A significance level,  $\alpha$ , of 0.05 will be used for statistical testing of the primary and secondary endpoints.

A hierarchical testing procedure will be applied to secondary efficacy analyses to control the overall type I error rate. In the case that the primary efficacy analysis is statistically significant at a 2-sided type I error rate of 0.05, the secondary efficacy endpoints will be tested at a 2-sided type I error rate of 0.05 in the order listed below. If any of the secondary endpoints are found to be not statistically significant at the 2-sided 0.05 level, the hypothesis testing will stop. Later endpoint(s) after a non-statistically significant result will be summarized descriptively and p-values may be produced for descriptive purposes only.

- Mean change in aggregate sensitivity of microperimetry within the EZ line break area from the Baseline Visit through the Month 24 Visit
- Mean change in reading speed from the Baseline Visit through the Month 24 Visit
- Mean change in the National Eye Institute Visual Function Questionnaire-25 (NEI-VFQ-25) near activities subscale score from the Baseline Visit through the Month 24 Visit

### Accounting for Missing Data:

Every attempt will be made to collect data per the protocol and to avoid missing data. As such, dropouts and missing data are expected to be minimal, but can inevitably occur. For cases with unavoidable missing data, no imputation will occur.

As the efficacy endpoints in this study are longitudinal, measured over the course of multiple observations over time, the minimum requirement for completion of the study is to have measurements at Baseline and Month 24, plus at least one interim visit for the primary efficacy endpoint. Imputation methods may be implemented for sensitivity assessments of primary and secondary efficacy analyses should the dropout rate and proportion of missing values be higher than expected or should there be missing data due to an identifiable cause unrelated to study procedures or treatments (e.g. delayed visits due to COVID-19).

#### Covariates and Subgroups:

There are no plans to adjust the primary efficacy analysis for baseline characteristics and disease status. Exploratory analyses will be conducted to assess the potential contribution of a number of baseline disease characteristics as well as study site on the likelihood of a response to treatment.

Exploratory analyses will be performed to assess the potential impact of various prognostic factors on efficacy. Appropriate statistical models will be fit with these factors as covariates and the effect of treatment will be assessed after adjusting for other significant risk factors. Risk factors will include, but are not limited to age, race, sex, and baseline EZ area.

## 12.2 SAMPLE SIZE

Sample size calculation is based on the comparison of the 2 groups over 24 months incorporating a longitudinal mixed effects model. The number of participants, N, in each of the 2 groups is calculated as follows: We assume that, in the NT-501 group, the response of change in EZ area is as follows:

$$Y_{ij} = \beta_{0 NT-501} + \beta_{1 NT-501}x_{ij} + \varepsilon_{ij}, \quad j = 1, \dots, n; i = 1, \dots, m$$

For the sham group the sham equation holds as follows:

$$Y_{ij} = \beta_{0 Sham} + \beta_{1 Sham}x_{ij} + \varepsilon_{ij}, \quad j = 1, \dots, n; i = 1, \dots, m$$

Both groups have the same number of participants (m),  $x_{ij} = x_j$  represents the duration between the first and the jth visit in which case  $\beta_{1 Sham}$  and  $\beta_{1 NT-501}$  represents the rates of change in Y for Sham and NT-501, respectively, and each person is measured at the same time points, and each participant has n repeated observations of EZ area at baseline, 12, 16, 20 and 24 months (where months will be converted to years).

The number of participants, m, in each of the 2 groups is calculated as follows:

$$m = \frac{2(z_{\alpha} + z_{\beta})^2 \sigma^2 (1 - \rho)}{ns_x^2 d^2}$$

where  $d = \beta_{1 Sham} - \beta_{1 NT-501}$  and  $s_x^2$  is the within-subject variance of  $x_j$ .

Using the above equation with a Type 1 error rate of 0.05 (2-sided);  $\sigma^2 = 0.0256$ ;  $\rho = 0.6$ ;  $s_x^2 = 0.47$  and  $n = 5$  (baseline and 12, 16, 20 and 24 months) we have 80% power with a sample size of 50 participants per treatment group to detect a difference in rate of change 0.037 mm^2/year in the EZ area in the NT-501 group versus the sham group. The sample size will be increased to 56 participants per treatment group (112 total participants) to provide adequate power in the analysis of the population evaluable for efficacy.

The statistical model will be a random intercept model as follows:

$$Y_{ij} = (\beta_0 + b_0) + \beta_1 * TRT + \beta_2 * TIME + \beta_3 * TRT * TIME + \varepsilon_{ij}$$

where  $Y_{ij}$  is the efficacy endpoint (EZ area) measurement for participant  $i = 1, 2, \dots, n$  at time point  $j = 1, \dots, K$ . TRT is an indicator of the participant  $i$ 's treatment group (ie, TRT = 1 for NT-501; TRT = 0 for sham) and TIME is the annualized time. To compare the rate of change from baseline in EZ area between the 2 treatment groups the primary hypothesis is as follows:

$$H_0: \beta_3 = 0 \text{ versus } H_1: \beta_3 \neq 0$$

## 12.3 STATISTICAL METHODS

### 12.3.1 Primary Endpoint(s)

The primary hypothesis is that NT-501 will slow the rate of change in the EZ (IS/OS) area loss. The primary efficacy endpoint will be analyzed using the mITT population (main analysis) but restricted to only those participants with at least 3 visits recorded. Baseline, Month 24, and at least one of Month 12, 16, or 20. A similar analysis will also be conducted with the PP Population.

The primary efficacy variable will be the rate of change that will be determined by using values from the EZ area as measured by SD-OCT. EZ area will be defined as the mean of 2 independent readings of the single eligible SD-OCT enface image taken at baseline and Months 12, 16, 20, and 24. A longitudinal mixed model will include EZ area as the dependent variable, a random intercept term to account for within subject variability, treatment group, time as a continuous variable, and the interaction between treatment and time. Time will be captured as the relative study day (defined as days since date of surgery) of the respective efficacy assessment and will include the days corresponding to the Baseline, Month 12, 16, 20, and 24 visits. The difference in the rate of change in EZ area over 24 months (to be computed by including baseline and Months 12, 16, 20, and 24 EZ measurements) will be compared using a random intercept model and the corresponding 95% confidence interval (CI), SE, test statistic, and p-value of the difference between treatment group parameters by computing the parameter estimate for the treatment by time interaction term. An Unstructured covariance structure will be implemented as with continuous time there will be a single parameter each for between and within participant variability.

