With the current study design, all participants will have a screening period of up to 30 days. During that time, a single baseline image of the EZ lesion will be taken to establish eligibility and the study baseline. The EZ line break area for eligibility will be determined by the reading center. Images will be reviewed for quality and may be repeated if necessary and obtained within the screening period (30 days). Two independent masked readers will determine lesion area from a single acceptable image. If the 2 estimates of area are within 10% and at least 1 measure is  $\geq 0.16$  and  $\leq 2.0$  mm^2, the MacTel lesion will be deemed eligible. If the 2 readings differ by more than 10%, an arbitrating reader will estimate the area. If the third reading is within 10% of either of the first 2 estimates, then the third and selected primary readings will be used to establish eligibility. Baseline EZ area will be the mean of the 2 qualifying estimates.

The implant surgery/sham procedure in the study eye should be completed within 30 days of randomization and/or up to 58 days from screening. Only 1 study-eligible eye of each participant will be designated as the study eye. Participants will be randomized (1:1) to receive the NT-501 implant or to undergo the sham procedure in the study-eligible eye. The implant surgery/sham procedure will occur on Day 0. Participants will be assessed on Day 1, Week 1 ( $\pm 2$  days), Month 1 ( $\pm 7$  days), Month 3 ( $\pm 14$  days), Month 6 ( $\pm 30$  days), Month 12 ( $\pm 30$  days), Month 16 ( $\pm 30$  days), Month 20 ( $\pm 30$  days), and Month 24 ( $\pm 30$  days). Note that, in regions other than France, a telephone contact will be made at Month 1 ( $\pm 7$  days) and Month 3 ( $\pm 14$  days) instead of a clinic visit. A subset of participants, based on the date of the surgical procedure, will be assessed at Month 36 ( $\pm 30$  days) and Month 48 ( $\pm 30$  days). Upon completion of the 24, 36, or 48-month observation, all participants will be followed for safety and disease progression in a nested substudy of the existing Natural History and Observation and Registry Study of Macular Telangiectasia Type 2 (NHOR).

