## 7.2 STUDY VISIT PROCEDURES

### 7.2.1 Screening/Baseline Procedures (Visit -1)

Screening procedures may be completed over more than 1 visit to accommodate schedules and to lessen participant burden. All screening evaluations should be completed within 30 days of the initial screening visit in order to be used to establish eligibility.

In the event that a participant is rescreened and the rescreening occurs within 6 months of the initial screening, fluorescein angiography, fundus autofluorescence imaging, and color fundus photography will not be repeated; the participant's initial screening results for each of these assessments will be used as their baseline.

Once the individual has indicated interest in participation, the principal investigator or appropriate designee must obtain the participant's written consent. Once the consent is obtained, the participant may initiate screening assessments. The results of all screening evaluations must be reviewed and the participant must be found eligible prior to randomization. Once a participant is determined to be eligible for the study, surgery should be completed within 4 weeks of randomization and/or up to 58 days from screening.

The screening examinations and imaging must include the following:

- Medical evaluation, standard for any surgical procedure or anesthesia (the specific tests to be ordered will be site-specific), may be performed on the day of surgery
- Demographics; medical and ophthalmic history
- Concomitant medications
- NEI-VFQ-25
- Reading speed
- Manifest refraction
- BCVA
- Goldmann applanation tonometry
- Measurement of undilated pupil diameter
- Slit-lamp biomicroscopy
- Microperimetry
- Dilated fundus examination
- SD-OCT
- Fluorescein angiography
- Fundus autofluorescence imaging
- Color digital fundus photography
- Urine pregnancy test for female participants of childbearing potential

The study investigator at each site, in conjunction with the reading center (SD-OCT, fluorescein angiography), will evaluate potential participants for study enrollment according to the inclusion and exclusion criteria as outlined in Sections 5.2 and 5.3.

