5 SAMPLE SIZE CONSIDERATIONS

Sample size calculation is based on the comparison of the 2 groups over 24 months (720 days) incorporating a longitudinal mixed effects model. The number of participants, N, in each of the 2 groups [15] is calculated as follows: We assume that, in the NT-501 implant group, the response of change in EZ area is as follows:

$$Y_{ij} = \beta_{0NT-501} + \beta_{1NT-501}x_{ij} + \varepsilon_{ij}, \quad j = 1, \dots, n; i = 1, \dots, m$$

For the sham group the sham equation holds as follows:

$$Y_{ij} = \beta_{0Sham} + \beta_{1Sham}x_{ij} + \varepsilon_{ij}, \quad j = 1, \dots, n; i = 1, \dots, m$$

Both groups have the same number of participants (m), $x_{ij} = x_j$ represents the duration between the first and the jth visit in which case β_{1Sham} and $\beta_{1NT-501}$ represents the rates of change in Y for Sham and NT-501 implant, respectively, and each person is measured at the same time points, and each participant has n repeated observations of EZ area planned to occur at baseline, 12, 16, 20 and 24 months (where months will be converted to years).

The number of participants, m, in each of the 2 groups [15] is calculated as follows:

$$m = \frac{2(z_{\alpha} + z_{\beta})^2 \sigma^2 (1 - \rho)}{ns_x^2 d^2}$$

where $d = \beta_{1Sham} - \beta_{1NT-501}$ and s_x^2 is the within-subject variance of x_j .

Using the above equation with a Type 1 error rate of 0.05 (2-sided); variance of endpoint (σ^2)= 0.0256; correlation between within participant observations (ρ) = 0.6; $s_x^2 = 0.47$ and n = 5 (baseline and 12, 16, 20 and 24 months) we have 80% power with a sample size of 50 participants per treatment group to detect a difference in rate of change 0.037 mm²/year in the EZ area in the NT-501 implant group versus the sham group. The sample size will be increased to 56 participants per treatment group (112 total participants) to provide adequate power in the analysis of the population evaluable for efficacy.

The statistical model will be a random intercept model as follows:

$$Y_{ij} = (\beta_0 + b_{0i}) + \beta_1 * TRT + \beta_2 * TIME + \beta_3 * TRT * TIME + \varepsilon_{ij}$$

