9 EFFICACY EVALUATION

9.1 Primary Efficacy Analysis

The primary hypothesis is that the NT-501 implant will slow the rate of change in the EZ (IS/OS) area loss. The primary efficacy endpoint will be analyzed using the mITT Population but restricted to only those participants with at least 3 visits recorded: Baseline, Month 24, and at least one of Month 12, 16, or 20 visits. An analysis will also be conducted with the PP Population with the same restriction to only participants with at least 3 visits recorded: Baseline, Month 24, and at least one of Month 12, 16, or 20 visits.

The primary efficacy variable will be the rate of change that will be determined by using values from the EZ area as measured by SD-OCT. EZ area will be defined as the mean of 2 independent readings of the single eligible SD-OCT enface image taken at Baseline and at Months 12, 16, 20, and 24. A longitudinal mixed model will include EZ area as the dependent variable, a random intercept term to account for within subject variability, treatment group, time as a continuous variable, and the interaction between treatment and time. Time will be captured as the relative study day of the respective efficacy assessment and will include the days corresponding to the Baseline, Month 12, 16, 20, and 24 visits. The difference in the rate of change in EZ area over 24 months will be computed by including Baseline, Months 12, 16, 20, and 24 EZ measurements, will be compared using a random intercept model and the corresponding 95% confidence interval (CI), SE, test statistic, and 2-sided p-value of the difference between treatment group parameters by computing the parameter estimate for the treatment by time interaction term. An unstructured covariance structure will be implemented as with continuous time there will be a single parameter each for between and within participant variability.

Prior to the analysis, out of window visits will be incorporated as noted in Section 7.5. With a mixed effects model as the primary analysis model, no imputation of missing data will be done.

As stated in Section 7.6, it may be determined prior to study end and database lock that the most appropriate parameterization of time is as a categorical variable. If this occurs, the modification to the

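### The primary slope starts at a pre-surgery scan while time runs from surgery, so the treatment-by-time estimate is slightly diluted (about 2-6% for assumed mean gaps of 14-44 days, ceiling about 8%)

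*Protocol*

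**What the plan says.** **Source of the baseline.** Protocol 4.1 says that in the screening period "a single baseline image of the EZ lesion will be taken to establish eligibility and the study baseline". SAP 7.1 takes the latest non-missing screening value as baseline. The Schedule of Events lists SD-OCT at Screening/Baseline and next at Month 6, with none on Day 0.

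**Time from scan to surgery.** Protocol 4.1 says the procedure "should be completed within 30 days of randomization and/or up to 58 days from screening". Protocol 6 and 7.2.2 agree. Protocol 7.2.1 says "surgery should be completed within 4 weeks of randomization and/or up to 58 days from screening", and Protocol 4.1.3 and SAP 4.1 also use 4 weeks.

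**Time in the model.** Protocol 12.3.1: "Time will be captured as the relative study day (defined as days since date of surgery) of the respective efficacy assessment". SAP 9.1: "Time will be captured as the relative study day of the respective efficacy assessment and will include the days corresponding to the Baseline", with relative study day defined in SAP 7.5 as days since surgery.

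**Treatment in the model.** Protocol 12.2 and SAP 5 define TRT as a fixed arm indicator. The tested parameter is the coefficient of TRT × TIME in a random-intercept model.

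Neither document sets the baseline day to zero or starts the treatment slope at surgery. None of the four sensitivity analyses in SAP 9.1.1 keeps a rate and starts the treatment effect at surgery.

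**The concern.** An implant cannot act before it is implanted, so the arms should differ only from Day 0. The planned interaction is a straight line through every scan, including the one on a negative day. It therefore spreads the divergence over the untreated interval as well, and the fitted slope difference is smaller than the difference in rate after surgery. The amount depends on how long participants waited for surgery, which has nothing to do with the device. The coefficient and its 95% CI are the trial's main result, so even a modest, one-directional distortion deserves attention if it is cheap to remove.

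**Working it through.** **Inputs.** Protocol 12.2 claims "80% power with a sample size of 50 participants per treatment group to detect a difference in rate of change 0.037" mm²/year at two-sided 0.05. SAP 5 gives "variance of endpoint (σ^2)= 0.0256". Both give ρ = 0.6, s_x² = 0.47 and n = 5 scans. One month is 30 days (Protocol 4.1), so the post-surgery scans fall on days 360, 480, 600 and 720. The scan-to-surgery gap L is not given and is varied.

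**Step 1: reproduce the plan's figure.** σ²(1−ρ) = 0.0256 × 0.4 = 0.01024.

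m = 2 × (1.960 + 0.842)² × 0.01024 / (5 × 0.47 × 0.037²) = 49.97, so 50 per arm, as stated. The variance of (0, 1, 1.333, 1.667, 2) years is 0.471, which matches 0.47. The calculation therefore assumes no gap.

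**Step 2: dilution.** Let the true difference between arms be d × max(0, t), with equal progression before surgery. With a random intercept and common visit times, the planned interaction estimates d × r, where

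r = Σ(t − t̄) max(0, t) / Σ(t − t̄)², with t = (−L, 360, 480, 600, 720).

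For L = 58:
- t̄ = (2,160 − 58)/5 = 420.4
- numerator = 1,238,400 − 420.4 × 2,160 = 330,336
- denominator = 1,238,400 + 3,364 − 5 × 420.4² = 358,083
- r = 0.9225

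| Gap L (days, all participants) | r | Estimate when the true value is 0.037 | s_x² | Power, 50 per arm |
|---|---|---|---|---|
| 0 | 1.000 | 0.0370 | 0.471 | 80.1% |
| 14 | 0.980 | 0.0363 | 0.490 | 80.1% |
| 30 | 0.959 | 0.0355 | 0.512 | 80.1% |
| 44 | 0.940 | 0.0348 | 0.532 | 80.1% |
| 58 | 0.923 | 0.0341 | 0.553 | 80.05% |

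Fitting the random-intercept model to simulated data gave a ratio of 0.923 with every gap at 58 days, and 0.945 with gaps uniform on 14-58 days.

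**Step 3: why power does not move.** The longer time span raises s_x² and lowers the standard error almost in step with the estimate. The SE is √(2 × 0.01024 / (50 × 5 × s_x²)), which is 0.01319 at L = 0 and 0.01218 at L = 58. Estimate over SE is 0.0370/0.01319 = 2.81 and 0.0341/0.01218 = 2.80.

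**Step 4: the alternative term.** With TIME kept for the common slope and TRT × max(0, days since surgery) as the interaction, exact generalised least squares returns 0.0370 at every gap. Power is 80.1-80.2% for gaps up to 58 days.

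**Step 5: the other possible coding.** If baseline were coded as Day 0, the between-arm ratio would be 1.0, but both arm slopes would be overstated, because growth before surgery would be assigned to no elapsed time.

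**The case against.** - **Estimand.** The endpoint is worded as the rate from the Baseline Visit, and the planned slope estimates that. This stands: the shrinkage is relative to the post-surgery rate, which the documents do not name as the target. That rate is still the natural reading of a hypothesis that the implant slows EZ loss.
- **Size.** The shift is 0.0015 mm²/year at 30 days and 0.0029 at 58. Against an SE of about 0.013, that is about 0.1 and 0.2 SE, toward zero. This stands.
- **Existing cover.** The categorical-time sensitivity model (SAP 9.1 and 9.1.1) compares arms at Month 24 by visit label, so the negative day does not enter. This stands in part: that model gives a difference at one visit, and the headline rate stays diluted.
- **Onset.** Starting the interaction at Day 0 assumes an immediate, constant effect, which no passage supports. True, but the planned term assumes an effect before surgery. With an assumed 60-day lag and a 58-day gap, the alternative gives 0.0339 and the planned term 0.0312, against a true 0.037. The alternative is still closer.
- **Different time origins.** Protocol 12.2 measures x from the first visit. A reader might take this as a further error, but shifting a participant's origin leaves the slope unchanged, and power is about 80% at every gap in the table.

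**Conclusion.** The point holds as a small matter of accuracy. For assumed mean gaps of 14-44 days, the primary estimate understates the post-surgery rate difference by about 2-6%. The ceiling is about 8%, reached only if every participant had a 58-day gap. This rests on an effect that starts at surgery, equal progression in both arms before it, and baseline keeping its negative study day, which is the literal reading.

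Three stronger readings are not supported:

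- **That the result is off by 8%.** The actual gaps are not given, and the image may be taken or repeated at any time in the 30-day screening period, so the gap can be well under the limit.
- **That the test is compromised.** Neither arm is treated before surgery, so type I error is not raised, and power is essentially unchanged. The direction is conservative.
- **That the loose wording on timing leaves the dilution unlimited.** Protocol 5.4 separately limits screening to 30 days. Thirty days plus 30 to surgery is 60, where the dilution is 8.0%. A longer gap would need a delay between the end of screening and randomisation that the documents do not describe. The difference between 28 and 30 days moves the figure by only about 0.25 percentage points.

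**What to change.** 1. In Protocol 12.3.1 and SAP 9.1, keep TIME as days since surgery for the common slope and define the interaction as TRT × max(0, days since surgery). Test and report that coefficient. If the primary model is to stay as it is, prespecify this term as a sensitivity analysis alongside the categorical-time model.
2. State explicitly how the baseline day is coded.
3. Tabulate the scan-to-surgery gap by arm, so that readers can see how much dilution applies.
4. Reconcile the passages on surgery timing (Protocol 4.1, 4.1.3, 6, 7.2.1 and 7.2.2; SAP 4.1), which differ between 30 days and 4 weeks and share an ambiguous link to the 58-day limit. Which limit applies is for the sponsor to decide.

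The cost is one derived variable, a sentence or two in each document before database lock, and wording the estimand as the post-surgery rate. No new data are needed and no power is lost.
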